## 6.4.1.5. Cardiac Monitoring

## 6.4.1.6. Cardiac Monitoring and Dose Modification Guidelines

In Study 208850 examining GSK3745417 in participants with advanced solid organ tumors, one case of immune-mediated perimyocarditis has been observed, with a likely causal relationship to GSK3745417. On-study monitoring of cardiac symptoms (myocarditis or pericarditis), troponins and cardiac function (using ECHO or MUGA) will be therefore required in this study.

BNP will be measured at screening and then on study as clinically indicated. Troponin should be measured at baseline and then every 2-3 weeks on study as per the schedule in Section 1.3. Troponin T will be assessed at a central laboratory as a means of consistent evaluation across all subjects. A second troponin sample will be assessed at a local laboratory for purposes of subject management. Whenever possible, troponin T will be assayed by the local laboratory. However, troponin I may be assessed at a local laboratory if troponin T is not available. The same local laboratory test (troponin I or troponin T) should be used consistently for an individual subject throughout the study.

Participants should receive a screening ECHO which should be a 3D ECHO if available. If not, a 2D ECHO should be used, and MUGA may be used where ECHO is considered sub-optimal e.g., large body habitus. The same modality should then be used throughout the study to enable comparison to baseline (ideally by the same reader at study center). Global longitudinal strain will be assessed via ECHO. All ECHO/MUGA data will be transferred and reviewed by an independent cardiologist.

GSK3745417 should be withheld, and participant referred for cardiology consult if:

- Troponin is elevated  $\geq 2 \times ULN$
- patient experiences symptoms consistent with pericarditis or myocarditis
- ECHO on-study decrease in left ventricular ejection fraction ≥ 10% AND falling below the LLN, OR
- Absolute decrease in left ventricular ejection fraction  $\geq 15\%$ , even if LVEF remains in the normal range for the institution

Elevation of troponin  $\geq 2 \times$  ULN without symptoms requires withholding GSK3745417 while awaiting repeat troponin value. A repeat troponin  $\geq 2 \times$  ULN requires withholding GSK3745417 and awaiting cardiology consult. In participants with asymptomatic troponin elevations, GSK3745417 may be restarted in discussion with medical monitor, depending on benefit/risk.

Participants with suspected myocarditis should be diagnosed and managed in line with institutional guidelines and cardiology advice. For a detailed review of diagnosis and management of myocarditis, and to guide treatment principles, the ASCO guidelines (Brahmer, 2018) and a recent review of myocarditis in patients treated with checkpoint

inhibitors (Palaskas, 2020) may be used, which include treatment principles around use of high dose steroids with a slow, monitored taper.

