# 1.3.1. Part 1 – Dose Escalation

# Table 1 Schedule of Activities: Part 1 - Dose Escalation Cohort(s)

DE Cohort	Screening a	Screening a Cycle (Induction Period)		on Period)	Follow-Up (post-final dose administered)		
Study Procedure		Interven (In-F	tion Period Patient)	Observation Period (Outpatient)	TDV⁵	Follow- Up	Notes
Week	≤4	1	- 2	3 - 4	+4		
Day	≤28	-1	1 - 13	14 - 28	+30d		
Informed Consent	Х						
Inclusion and Exclusion criteria	X						
Demographics, Medical History, Prior Medications, Disease Characteristics	x						Include use of antibiotics, probiotics and anti-infectives taken 60 days prior to study intervention.
Anticancer Therapy and Response to Prior Anticancer Therapy	x						
Participant Registration	x						
Safety Assessments		-	-				
In-House Monitoring		х	x				Participants should be monitored in a medically qualified unit/clinic/hospital starting on Day -1 through Day 13 (24 hours after the administration of GSK3745417 on Day 12) of each cycle.
Physical Exam	X		x		х		A complete physical exam is required at screening, including cardiac and neurological examinations; brief or targeted physical exams will be performed on Day 1 at predose (within 1h prior to dosing) and

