## CONFIDENTIAL

DE Cohort	Screening a	Cycle (Induction Period)			Follov (post-fina adminis	v-Up al dose stered)	
Study Procedure		Intervention Period (In-Patient)		Observation Period (Outpatient)	TDV⁵	Follow- Up	Notes
Week	≤4	1	- 2	3 - 4	+4		
Day	≤28	-1	1 - 13	14 - 28	+30d		
							sample, Days 8 - 12 – at EOI+6hrs: Day 13 – single sample prior to discharge. Clinical chemistry including uric acid and phosphate will be measured at least every 6 hours for the first 48 hours following initiation of daily dosing period, then at least twice daily up to an including Day 5 dosing of each daily dosing period, and more frequently as clinically indicated. Clinical chemistry samples should be collected more frequently if clinically indicated (such as cases of TLS). A sample will also be taken between Day 20 and Day 22 during the outpatient period of the cycle. See Section 10.2 for complete list of required laboratory assessments.
C-Reactive Protein	x		Х	Х	х		Sample collection times: Day 1 at predose, EOI+8h and +24h for first dose, then pre dose at Day 5 and Day 12 of each cycle.
Thyroid function c	X		Х		x		Sample collection times: Day 1 at predose of Cycles 1 and 3.
Troponin I and T	х		Х		Х		See Section 6.4.1.5 for management of cardiac events. Samples will be collected on Day 13.
BNP (or NTproNBNP)	Х	Repeat as clinically indicated					Repeat test as outlined in management of cardiac events (Section 6.4.1.5)
eGFR	Х						See Section 7.1.2 for management of renal events (if needed).

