#### CONFIDENTIAL

- a. All assessments performed at Screening must be performed within 28 days prior to first dose unless otherwise specified.
- b. The assessments required at the study treatment discontinuation visit must be completed within 30 days from the date study treatment was discontinued and must occur prior to the start of subsequent anti-cancer therapy; the window for this visit is +10 days.
- c. Procedures scheduled on study treatment administration days can be performed within 3 days prior to dosing day, unless otherwise specified.

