### CONFIDENTIAL

Q1W Cohort	Study Mair	ntenance Period			
Study Procedure	GSK417	Weekly (Q1W)	TDVª	Follow-Up (post-final dose administer ed	Notes
Week		1 and Thereafter	+4		
Day	-1	1 and Thereafter	+30d		
Safety Laboratory As	sessments				
Pregnancy Test		х	x	x	Urine pregnancy test will be conducted every 4 weeks for duration of study, on last day of treatment (if possible), at TDV, and at the Follow-Up visit.
CBC with differential	Х	Q1W	x		Sample collection times: Day –1 (single sample) and Day 1 at predose, EOI+4h and EOI+24h. At least every 6 hours for the first 48 hours following initiation of daily dosing period, then at least twice daily up to an including Day 5 dosing of each daily dosing period, and more frequently as clinically indicated.
Clinical Chemistry and TLS labs	х	Q1W	x		Sample collection times: Day –1 (single sample) and Day 1 at predose, EOI+6h, +12h, +18h and +24h; see Section 10.2 for complete list of required laboratory assessments.
C-Reactive Protein		Q1W	x		Sample collection times: predose, EOI+8h, and EOI+24h.
Thyroid function b		Day 1, then Q8W	X		The first assessment should be done at Week 1 and then Q8W.
Troponin I and T		Q2W	X		Sample will be collected predose and every 2 weeks.
BNP (or NTproNBNP)	X	Repeat as clinically indicated			Repeat test as outlined in management of cardiac events (Section 6.4.1.5)

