### CONFIDENTIAL

Q3W Cohort	Stu	dy Maintenance Period			
Study Procedure	GSK417 Every 3 Weeks (Q3W)		TDV⁵	Follow-Up (post- final dose administered	Notes
Week		1 and Thereafterª	+4	Q4W	
Day	-1	1 and Thereafter	+30d		
Concomitant Medication Review		Continuous: Asse	ss at ea	ch visit from first dose	of study intervention
Follow-Up Phone Call		Х			Participants should be contacted by phone 24-72 hours following discharge from clinic to assess for any AEs or cytokine related events
Safety Laboratory As	sessm	ents			
Pregnancy Test		Х	Х	Х	Urine pregnancy test will be conducted every 3 weeks for duration of study, on last day of treatment (if possible), at TDV, and at the Follow-Up visit.
CBC with differential	х	Q3W	х		Sample collection times: Day –1 (single-sample) and Day 1 at predose, EOI+4h and EOI+24h. At least every 6 hours for the first 48 hours following initiation of daily dosing period, then at least twice daily up to an including Day 5 dosing of each daily dosing period, and more frequently as clinically indicated.
Clinical Chemistry and TLS labs	х	Q3W	x		Sample collection times: Day –1 (single-sample) and Day 1 at predose, EOI+6h, +12h, +18h and +24h; see Section 10.2 for complete list of required laboratory assessments.
C-Reactive Protein		Q3W	Х		Sample collection times: Predose, EOI+8h, and EOI+24h.
Thyroid function b		Day 1, then Q6W	Х		The first assessment should be done at Week 1 and then Q6W.
Troponin I and T		Q3W	Х		Sample will be collected predose and every 3 weeks.
BNP (or NTproNBNP)	х	Repeat as clinically indicated			Repeat test as outlined in management of cardiac events (Section 6.4.1.5)
Urinalysis b		Q3W	Х		If urinalysis is abnormal, a microscopy should be performed.
Coagulation b		Day 1, then Q3W			The first assessment should be done at Day 1 and then Q3W.

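### Induction Tables 1 and 2 schedule troponin 28 days apart, while Section 6.4.1.6 asks for it every 2-3 weeks

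*Protocol*

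**What the plan says.** Protocol Section 6.4.1.6 makes on-study cardiac monitoring a requirement because one perimyocarditis case, with a likely causal link to the drug, occurred in Study 208850. It sets the frequency: "Troponin should be measured at baseline and then every 2-3 weeks on study as per the schedule in Section 1.3". Troponin T goes to a central laboratory for consistent evaluation across participants, and in addition "A second troponin sample will be assessed at a local laboratory for purposes of subject management". A result drives dosing even in someone who feels well: a value of at least 2 × "ULN without symptoms requires withholding GSK3745417 while awaiting repeat troponin value".

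The Section 1.3 tables then give the schedule:

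- **Tables 1 and 2 (induction, Parts 1 and 2).** Troponin is marked at screening, in the Day 1-13 column and at the treatment discontinuation visit. The Day -1 and Day 14-28 columns are empty. The note reads: "See Section 6.4.1.5 for management of cardiac events. Samples will be collected on Day 13".
- **Table 3 (weekly maintenance).** "Sample will be collected predose and every 2 weeks".
- **Table 4 (maintenance every 3 weeks).** "Sample will be collected predose and every 3 weeks".

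In the In-House Monitoring row of Table 1, Day 13 is "24 hours after the administration of GSK3745417 on Day 12) of each cycle", so it follows the tenth and last dose of the cycle.

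**The concern.** The sentence in Section 6.4.1.6 states an interval and says that Section 1.3 provides it. For induction, Section 1.3 does not. A site that follows Table 1 samples less often than the text asks, and a site that follows the text needs a sample that no table lists. The note in Tables 1 and 2 does not settle this, because it refers to Section 6.4.1.5, which is a heading with no text.

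The schedule is also sparsest where dosing is densest. An induction cycle has 10 doses and one scheduled troponin. Weekly maintenance has one troponin per two doses, and maintenance every 3 weeks has one per dose. No reason is given for the difference.

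At stake is the withhold step for a raised troponin without symptoms, which can work only if people without symptoms are sampled. Section 1.1 allows the dose to double for Cycle 2 and again for Cycle 3 in Part 1. The escalation criteria in Sections 4.1.2 and 6.4.1.1 name no troponin check. Section 4.1.2 relies on the safety and laboratory data that are available, and the only scheduled on-study troponin available is the Day 13 value.

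**Working it through.** **Inputs**

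- Required on-study interval: 2-3 weeks, or 14-21 days (Protocol Section 6.4.1.6).
- Induction cycle length: 28 days (Section 4.1, Part 1).
- Cycles: 3 (Sections 1.3 and 4.1).
- On-study induction troponin: Day 13 (Tables 1 and 2).
- Admission on Day -1 of each cycle (Table 6). There is no Day 0.

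**Step 1: can the stated interval be found in the tables?** Table 3 gives 14 days and Table 4 gives 21 days, so both agree with the text. Tables 1 and 2 need calculation.

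**Step 2: induction gaps.** Day d of cycle k is study day 28(k - 1) + d.

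- Cycle 1: 28 × 0 + 13 = study Day 13
- Cycle 2: 28 × 1 + 13 = study Day 41
- Cycle 3: 28 × 2 + 13 = study Day 69

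The gaps are 41 - 13 = 28 and 69 - 41 = 28 days. The excess over the upper limit is 28 - 21 = 7 days. Counted from the Cycle 1 sample, the next is due between study Day 13 + 14 = 27 and study Day 13 + 21 = 34. The table's next sample is on Day 41.

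**Step 3: age of the result at the next dose.** Cycle 2 Day 1 is study Day 29, and 29 - 13 = 16 days. The same holds from Cycle 2 to Cycle 3 (57 - 41 = 16).

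**Step 4: move to maintenance.** If weekly maintenance starts on study Day 85, the gap from Cycle 3 Day 13 is 85 - 69 = 16 days, which is within the interval. The conflict is confined to induction.

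**Step 5: effect of adding Day -1.** Day -1 of Cycle 1 is the day before Day 1. Day -1 of Cycle 2 is study Day 28.

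- Day -1 to Day 13: 1 + 12 = 13 days
- Day 13 to the next Day -1: 28 - 13 = 15 days
- Check: 13 + 15 = 28

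Both gaps are within 21 days, and the latest result is 1 day old at each Day 1 dose instead of 16. A Day 1 predose sample would also meet the interval (gaps of 12 and 16 days), but the tables define predose as within 60 minutes of injection, which leaves little time for a result.

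**The case against.** **The text defers to the tables.** The sentence says troponin should follow Section 1.3, so a site can reasonably treat the tables as governing, and one sample after each 10-dose block is a defensible design. That is fair as far as it goes. It does not remove the stated interval, which the induction tables miss. Rewording Section 6.4.1.6 to match the tables would cure the inconsistency, but the latest value would still be 16 days old at a dose that may be doubled.

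**Other monitoring exists.** A reader might infer that cardiac toxicity goes unwatched in induction. The documents do not support that. A raised Day 13 value triggers a hold before the next cycle. Suspected CRS triggers daily troponin for the first week and about every other day after that (Section 6.4.1.4). ECGs are taken on Days 1 and 4 of each cycle, Holter monitoring runs in Cycle 1, and the echocardiogram row calls for a study in the final observation week, with its own ejection-fraction triggers in Section 6.4.1.6. None of these is a scheduled troponin in a person without symptoms, so the gap narrows but does not close.

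**Three stronger readings fail.**

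- *A 40-day gap from screening.* Under footnote a of Table 1, "All assessments performed at Screening must be performed within 28 days prior to first dose unless otherwise specified", so screening to the first on-study sample can be 28 + 12 = 40 days. Up to 28 of those days precede any drug. Day 13 is only 12 days after the first dose, so this is not a breach of an on-study interval.
- *Too few samples in total.* Three samples in 84 days looks short, but the required number depends on where counting starts. Counted from Day 1, a 3-week interval falls on study Days 22, 43 and 64, which is also three; a 2-week interval falls on Days 15, 29, 43, 57 and 71, which is five. At the 3-week limit there is no shortfall in number. The spacing is the issue.
- *A mid-cycle sample is required.* Day 13 comes too late to stop any dose in its own cycle. That is a separate design choice, and the 2-3 week interval does not require a sample before Day 8.

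**Practical effect is limited.** SAP Section 4.8 reports that the study was terminated as Part 1 finished recruitment and that Part 2 did not recruit. The SAP names no troponin analysis, so no planned result changes. This stands.

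**Conclusion.** The inconsistency is real and confined to induction. Tables 1 and 2 give on-study gaps of 28 days against a stated 14-21, an excess of 7 days, and leave a 16-day-old value at the next cycle's first dose. The exposed case is narrow: a rise that begins after Day 13, without symptoms and without suspected CRS.

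This rests on two assumptions. Cycles follow one another without delay; a delayed cycle lengthens both figures. The Day 13 note applies to every cycle, as its place in a per-cycle column implies; read as Cycle 1 only, the gap would be longer.

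Because Part 2 did not recruit, the gap in practice applied to Part 1. It is a safety-monitoring correction worth making and does not threaten an endpoint or an analysis. One loose end remains for reporting: SAP Section 6.1.3 lists important deviations, and the protocol leaves unclear whether following Table 1 departs from Section 6.4.1.6. The sponsor should state which instruction governed.

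**What to change.** In the Troponin rows of Tables 1 and 2, replace the Day 13 sentence of the note with: *Troponin is taken on Day -1 and Day 13 of each cycle (local and central), and the local Day -1 result is reviewed before the Day 1 dose.* Point the note to Section 6.4.1.6 instead of the empty Section 6.4.1.5. The interval in Section 6.4.1.6 can then stand as written. Taking both assays on Day -1 matters: a local sample alone would leave central troponin T at 28-day gaps. The Day -1 value before Cycle 1 would also become the laboratory baseline under SAP Section 4.1.2, as the latest pre-dose value.

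The cost is one extra paired local and central sample per cycle, or 3 per participant over 3 cycles. No visit is added: participants are admitted on Day -1 and already have a CBC drawn then. The documents give no troponin tube volume and no volumes for most other draws, so the sponsor should check the addition against the limit of 275 mL in 4 weeks (Protocol Section 8). Review before dosing may mean a short wait for the local result on Day 1. For this closed study the change cannot alter conduct; it applies if the schedule is reused.

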## 6.4.1.7. Immune mediated events on study

In Study 208850 examining GSK3745417 in participants with advanced solid organ tumors, one case of immune-mediated perimyocarditis has been observed, with a likely causal relationship to GSK3745417. Participants with new cardiac or respiratory symptoms should be assessed for potential pericarditis or myocarditis, with cardiology consult and cardiac imaging as clinically indicated. Other immune-mediated events may be a potential risk of GSK3745417 based on the anticipated pharmacology.

## Table 12 Dose Modification and Toxicity Management Guidelines for Immune Related- Aes

General instructions: 1. Corticosteroi 2. For severe a by corticoste	d taper may be initiat nd life-threatening irA roids.	ed upon AE improving to Grade 1 or less as per invertex. AEs, IV corticosteroid should be initiated first followed	estigator judgement and institutional treatment gu d by oral steroid. Other immunosuppressive treat	idelines ment should be initiated if irAEs cannot be controlled
Immune-related Aes	Toxicity grade or conditions	Action taken±	irAE management with corticosteroid and/or other therapies	Monitor and follow-up
	(CTCAEv5.0)			
Pneumonitis	Grade 2	Restart dosing when toxicity resolves to Grade 0-1. If Grade 2 recurs, permanently discontinue.	
 
Administer corticosteroids (initial dose of 1-2 mg/kg methylprednisolone or
 
	
 
Monitor participants for signs and symptoms of pneumonitis
 

	Grade 3 or 4, or recurrent grade 2	Permanently discontinue	equivalent) followed by taper	
 
Evaluate participants with suspected pneumonitis with radiographic imaging and initiate corticosteroid treatment
 
Add prophylactic antibiotics for opportunistic infections
 

Diarrhea / colitis	Grade 2 or 3	Restart dosing when toxicity resolves to Grade 0-1.	Administer corticosteroids (initial dose of 1-2 mg/kg methylprednisolone or	
 
Monitor participants for signs and symptoms of enterocolitis (i.e., diarrhea, abdominal pain,
 

	Grade 4	Permanently discontinue	equivalent) followed by taper	
 
blood or mucus in stool with or without fever) and of bowel perforation (i.e., peritoneal signs and ileus).
 
Participants with ≥ Grade 2 diarrhea suspecting colitis should consider GI consultation and performing endoscopy to rule out colitis.
 
Participants with diarrhea/colitis should be advised to drink liberal quantities of clear fluids. If sufficient oral fluid intake is not feasible, fluid and electrolytes should be substituted via IV infusion.
 

AST / ALT elevation or increased bilirubin	Grade 2	Restart dosing when toxicity resolves to Grade 0-1.	Administer corticosteroids (initial dose of 0.5-1 mg/kg methylprednisolone or equivalent) followed by taper	Monitor with liver function tests (consider weekly or more frequently until liver enzyme value returned to baseline or is stable
	Grade 3 or 4	Permanently discontinue 	
 
Administer corticosteroids (initial dose of 1-2 mg/kg methylprednisolone or equivalent) followed by taper
 
	See Section 10.7 for additional details on Liver Event Follow-Up Assessments
Type 1 diabetes mellitus (T1DM) or Hyperglycemia	Grade 3-4 hyperglycemia or T1DM (associated with	Restart dosing in appropriately managed, clinically and metabolically stable patients; insulin replacement therapy is required.	
 
Initiate insulin replacement therapy for participants with T1DM
 
Administer antihyperglycemic in participants with hyperglycemia
 
	
 
Monitor participants for hyperglycemia or other signs and symptoms of diabetes.
 

General instructions: 1. Corticostero 2. For severe a by corticoste	bid taper may be initia and life-threatening ir eroids.	ated upon AE improving to Grade 1 or less as per invertex. AEs, IV corticosteroid should be initiated first follower	estigator judgement and institutional treatment gu d by oral steroid. Other immunosuppressive treat	uidelines tment should be initiated if irAEs cannot be controlled
Immune-related Aes	Toxicity grade or conditions	Action taken±	irAE management with corticosteroid and/or other therapies	Monitor and follow-up
	metabolic acidosis or ketonuria)β			
Hypophysitis	Grade 2 or 3	For Grade 2-3, hold until administration of hormonal therapy results in return to adequate hormone levels based on laboratory values and restart dosing when toxicity resolves to Grade 0-1. For recurrence or worsening of ≥ Grade 2 hypophysitis after steroid taper has been completed and patient is on adequate hormone replacement therapy, permanently discontinue.	
 
Administer corticosteroids and initiate hormonal replacements as clinically indicated.
 
	
 
Monitor for signs and symptoms of hypophysitis (including hypopituitarism and adrenal insufficiency)
 

	Grade 4	Permanently discontinue		
Hyperthyroidism	Grade 3	Hold until administration of hormonal therapy results in return to adequate hormone levels based on laboratory values and restart dosing when toxicity resolves to Grade 0-1.	Treat with non-selective beta-blockers (e.g., propranolol) or thionamides as appropriate	
 
Monitor for signs and symptoms of thyroid disorders.
 

	Grade 4	Permanently discontinue 		
Hypothyroidism	Grade 2-4	Grade 3: Hold until administration of hormonal therapy results in return to adequate hormone levels based on laboratory values and restart dosing when toxicity resolves to Grade 0-1.	
 
Initiate thyroid replacement hormones (e.g., levothyroxine or liothyroinine) per standard of care
 
	
 
Monitor for signs and symptoms of thyroid disorders.
 
Monitor TFTs
 
Ensure adequate evaluation (eg., endocrine
 

	Grade 3-4	Grade 4: Permanently discontinue		
 
consultation)
 
Exclude concomitant adrenal insufficiency (AM cortisol level)
 

Myocarditis or pericarditis	Grade 1 or 2	Withhold. Seek cardiology consult. Ensure complete resolution after steroid treatment before considering re-start of GSK3745417 depending on benefit/risk of further study drug	Based on severity of AE administer corticosteroids. Consider high dose steroids with slow taper, as per cardiology advice / institutional	Ensure adequate evaluation to confirm etiology and/or exclude other causes
	Grade 3 or 4	Permanently discontinue	
 
guidelines for myocarditis.
 
Treat until cardiac function returns to baseline
 
	

General instructions: 1. Corticostero 2. For severe a by corticost	oid taper may be initi and life-threatening i eroids.	ated upon AE improving to Grade 1 or less as per inver rAEs, IV corticosteroid should be initiated first followed	stigator judgement and institutional treatment gu by oral steroid. Other immunosuppressive treatr	idelines nent should be initiated if irAEs cannot be controlled
Immune-related Aes	Toxicity grade or conditions	Action taken±	irAE management with corticosteroid and/or other therapies	Monitor and follow-up
Adrenal insufficiency	(CTCAEv5.0) Grade 2 or 3	Hold until administration of hormonal therapy results in return to adequate hormone levels based on laboratory values and restart dosing when toxicity resolves to Grade 0-1. For recurrent or worsening ≥ Grade 2 adrenal insufficiency while adequate hormonal replacement is continuing, permanently discontinue study drug.	
 
Start treatment with corticosteroids before other hormone replacement to avoid adrenal crisis (hydrocortisone slowly titrating doses down according to symptoms OR prednisone and fludrocortisone titrating up or down based on BP, other symptoms, and labs); patient
 
	Monitor for cortisol level (AM), comprehensive metabolic panel (Na, K, CO  , glucose) and renin.
	Grade 4	Permanently discontinue	with severe symptoms may require additional fluids (e.g., saline >2 L).	
Uveitis	Grade 2	Withhold	
 
Urgent ophthalmology consultation
 
Administer treatment with ophthalmic and systemic prednisone/methylprednisolone
 
	Ensure adequate evaluation (e.g., urgent ophthalmology consultation)
Immune-related Encephalitis	Any grade	Permanently discontinue	
 
Consider IV acyclovir until PCR results obtained
 
Trial with methylprednisolone; if severe, treatment with methylprednisolone
 
If positive for autoimmune encephalopathy antibody or no improvement after 7-14 days, consider rituximab
 
	
 
Ensure adequate evaluation to confirm etiology and/or exclude other causes.
 

Rash	Grade 3	Withhold	
 
Treat with high potency topical steroids to affected areas
 
Treat with prednisone
 
	Ensure adequate evaluation (eg., urgent dermatology consultation) to confirm etiology and/or exclude other causes.
	Grade 4	Permanently discontinue		
Renal failure or nephritis	Grade 2	Restart dosing when toxicity resolves to Grade 0-1.	
 
Start treatment with prednisone; if persistent G2 beyond 1 week, prednisone/methylprednisone
 
	
 
Monitor participants for signs and symptoms, including monitoring of creatinine and urine protein every 3-7 days.
 
Ensure adequate evaluation (eg., nephrology consultation) to confirm etiology and/or exclude other causes.
 

General instructions:				

 
Corticosteroi
 
	id taper may be initia	ted upon AE improving to Grade 1 or l	ess as per investigator judgement and institutional treatment gui	delines
2. For severe a	nd life-threatening ir/	AEs, IV corticosteroid should be initiate	ed first followed by oral steroid. Other immunosuppressive treatr	nent should be initiated if irAEs cannot be controlled
by corticoste	roids.			
Immune-related Aes	Toxicity grade or conditions	Action taken±	irAE management with corticosteroid and/or other therapies	Monitor and follow-up
	(CTCAEv5.0)			
	Grade 3 or 4	Permanently discontinue	
 
Start treatment with prednisone; if persistent G2 beyond 1 week, prednisone/methylprednisone
 
Consider adding one of the following after 1 week of steroids: azathioprine, cyclosporine, cyclophosphamide, infliximab, mycophenolate
 
	
 
Ensure adequate evaluation (eg., nephrology consultation, renal biopsy) to confirm etiology and/or exclude other causes.
 
Consider inpatient care
 

Recurrence of Aes	Grade 1 or 2	Withhold	Based on severity of Aes, administer	
≤Grade 1	Grade 3 or 4	Permanently discontinue	appropriate treatment until symptoms improve to ≤Grade 2	
NOTES	•	•		

The decision whether to withhold or permanently discontinue GSK3745417 is at the discretion of the investigator or treating physician.
 For participants with Grade 3 or 4 immune-related endocrinopathy where interruption of GSK3745417 is required, treatment with GSK3745417 may be resumed when the event resolves to Grade ≤2 and is controlled with hormonal replacement therapy or, for T1DM, metabolic control has been achieved.

